##### *General potential confounders*

- Age (matching factor).
- Gender (matching factor).
- Calendar time (matching factor).
- Alcohol abuse (if available).
- Health seeking behaviour: number of visits to general practitioner or hospital contacts in the year before cohort entry/index date.
- Use of any drugs: number of different compounds used in the year previous to cohort entry/index date.

##### *Cardiovascular risk factors*

- Hyperlipidemia according to coded diagnoses or the presence of a raised level of total cholesterol or LDL cholesterol in medical records at cohort entry/index date (also precautionary condition).
- Use of lipid lowering agents (ATC C10) at cohort entry/index date.
- Smoking status (if available) at cohort entry/index date (precautionary condition).
- Type 2 diabetes mellitus: based on recorded diagnosis or use of oral anti-diabetic agents (ATC A10B) (precautionary condition) at cohort entry/index date.
- History of diagnosed obesity (if body mass index is unavailable) at cohort entry/index date.
- Diagnosis of chronic kidney disease (as recorded in medical records) at cohort entry/index date.
- Diagnosis of hypertension on or before cohort entry/index date.
- Use of antihypertensive drugs in the year prior to cohort entry/index date: alpha blockers (ATC C02CA), B-blockers (ATC C07), ACE inhibitors (ATC C09A/C09B), Angiotensin II inhibitors (ATC C09C/C09D), calcium channel blockers (ATC C08C)).
- Use of low-dose aspirin (ATC B01AC06) or clopidogrel (ATC B01AC04) in the year prior to cohort entry/index date.
- Previous use of anticoagulants in the year prior to cohort entry/index date: vitamin K antagonists (ATC B01AA), heparins (ATC B01AB), direct thrombin inhibitors (ATC B01AE), direct factor Xa inhibitors (ATC B01AF).

##### *Osteoporosis/Fracture risk factors*

- History of osteoporotic fracture as a proxy for osteoporosis severity (all but skull/face, fingers, and toes) prior to cohort entry/index date ([Appendix 14.3.1](#)).
- Previous use of anti-osteoporosis medications (ATC M05B) in the year prior to index date/cohort entry.
- Previous use of prescribed vitamin D supplements (ATC A11CC01, A11CC03, A11CC04, A11CC05, A11CC06, and A11CC20) in the year prior to index date/cohort entry.
- Previous use of prescribed calcium supplements (ATC A12AA01, A12AA02, A12AA03, A12AA04, A12AA05, A12AA06, A12AA07, A12AA08, A12AA09, A12AA10,

A12AA11, A12AA12, A12AA13, A12AA20, and A12AA30) in the year prior to index date/cohort entry.

- Previous use of prescribed calcium and vitamin D (concomitant) supplements (ATC A12AX) in the year prior to index date/cohort entry.
- Previous use of systemic glucocorticoids (ATC H02AB) in the year prior to index date/cohort entry.

#### 9.4. Data sources

This study will be conducted using routinely collected data from different data sources that participate in the EU-ADR Alliance. These databases provide representative clinical information as collected in actual practice conditions in different European healthcare settings. The proposed databases have been selected based on their geographic location, the availability of longitudinal population-based data on drug utilization, and their experience in previous multi-database studies on both drug utilization and safety. Five countries from different European areas (two from Southern Europe, two from Central Europe, and one Scandinavian nation) and with very different rates of use of SR (from lowest in Netherlands, to highest in Spain) are included in order to provide heterogeneous and representative data for the evaluation of the effectiveness of the RMM, as well as to guarantee sufficient statistical power for the comparative study. All of the participating databases are part of the EU-ADR alliance, a stable collaboration framework for running drug utilization and safety studies in a federated manner.

**Table (9.4) 1 - Overview of contributing databases**

Country	Netherlands	United Kingdom	Denmark	Italy	Spain
Name of the database	IPCI	THIN	Aarhus	HSD- Thales	SIDIAP
Type of database	MR	MR	ADM	MR	MR
# patients, millions	1.2	3.5	1.8	1.5	5.1
Age categories	All	All	All	>15 years	>15 years
Date in	Yes	Yes	Yes	Yes	Yes
Date out	Yes	Yes	Yes	Yes	Yes
Date death	Yes	Yes	Yes	Yes	Yes
Prescriptions					
Outpatient Rx	Yes (specialist incomplete)	Yes (specialist incomplete)	Yes	Yes (specialist incomplete)	Yes (specialist incomplete)
Coding of drugs	ATC	BNF/Multilex	ATC	ATC	ATC
Dosing regimen	Yes	Yes	No	Yes (incomplete)	Yes
Outcomes					
Hospitalizations	Yes	Yes	Yes	Yes	Yes
Outpatient diagnoses	Yes	Yes	Yes	Yes	Yes
Coding of disease	ICPC	READ	ICD-10	ICD-9 CM	ICD-10
Cause of death	Yes (from text)	If linked to death registry	Yes	No	No

*ADM = administrative; ATC = Anatomical Therapeutic Chemical; BNF = British National Formulary; ICPC = International Classification of Primary Care; MR = Medical Records*

All of the chosen databases comply with European Union (EU) guidelines on the use of medical data for medical research and have been validated for pharmaco-epidemiological research (Cazzola, 2011; Vlug, 1999).

The databases will be THIN (UK), HSD (Italy), IPCI (NL), the Aarhus University Database (DK) and SIDIAP (Spain). Table (9.4) 1 provides an overview of key elements of these databases. The total number of persons in the source population will be around 12 million as of 2012.

HSD (Italy), IPCI (Netherlands), SIDIAP (Spain) and THIN (UK) are listed under the ENCePP resources database: ([www.encepp.eu/encepp/resourcesDatabase.jsp](http://www.encepp.eu/encepp/resourcesDatabase.jsp)).

#### **9.4.1. IPCI Database**

In 1992 the Integrated Primary Care Information Project (IPCI) was started by the Department of Medical Informatics of the Erasmus University Medical Centre. IPCI is a longitudinal observational database that contains data from computer-based patient records of a selected group of general practitioners (GPs) throughout The Netherlands, who voluntarily chose to supply data to the database. Collaborating practices are located throughout The Netherlands and the collaborating GPs are comparable to other GPs in the country according to age and gender. In the Netherlands, all citizens are registered with a GP practice, which forms the point of care and acts as a gatekeeper in a two-way exchange of information with secondary care. The medical records of each patient can therefore be assumed to contain all relevant medical information including medical findings and diagnosis from secondary care. The IPCI database is representative for the Dutch population regarding age and gender (Voordouw, 2004).

The database contains information on about 1.5 million patients. This is the cumulative amount of patients who have ever been part of the dynamic cohort of patients who have been registered. The International Classification of Primary Care (ICPC) is the coding system for patient complaints and diagnoses, but diagnoses and complaints can also be entered as free text. Prescription data such as product name, quantity prescribed, dosage regimens, strength and indication are entered into the computer (Vlug, 1999). The National Database of Drugs, maintained by the Royal Dutch Association for the Advancement of Pharmacy, enables the coding of prescriptions, according to the ATC classification scheme recommended by the World Health Organization (WHO, 2008). Approval needs to be obtained for each study from the governance board.

#### **9.4.2. HSD – CSD Longitudinal Patient Database**

The Italian partner for the study will use the Health Search CSD Longitudinal Patient Database (HSD), a longitudinal observational database that is representative of the Italian general population. HSD was established in 1998 by the Italian College of General Practitioners (Filippi, 2005). The HSD contains data from computer-based patient records from a selected group of GPs covering a total of 1.5 million patients) located throughout Italy. These GPs voluntarily agreed to collect data for the database and attend specified training courses. The database includes information on the age, gender, and identification of the patient, and GP registration information, which is linked to prescription information, clinical events and diagnoses, hospital admission, and causes of death. All diagnoses are coded according to ICD-9-CM. Drug names are coded according to the ATC classification system (WHO, 2008). To be included in the study, GPs must have provided data for at least 1 year

and meet standard quality criteria pertaining to: levels of coding, prevalence of well-known diseases, and mortality rates (Cricelli, 2003). The HSD has been used as data source for a number of peer-reviewed publications on the prevalence of disease conditions, drug safety and prescription patterns in Italian primary care (Cazzola, 2011). Approval for use of data is obtained from the Italian College of General Practitioners for each study.

### 9.4.3. THIN Database

The Health Improvement Network (THIN) is a database of primary care medical records from the UK. General practitioners are trained to complete their medical records using the Vision general practice computer system (InPractice Systems, London, UK). This electronic record serves as the primary medical records for the practice.

Data recorded in THIN include demographics, details from GPs' visits such as medical diagnoses and prescriptions written by the GPs, diagnoses from specialist referrals and hospital admissions, some results of laboratory tests, some lifestyle characteristics and other measurements as taken in the practice. Within the database, diagnoses are recorded using READ codes. Prospective data collection for THIN began in September 2002, with electronic medical records that date back to 1985. In addition, practices may retrospectively enter significant medical events into the electronic medical record. Currently, the database has 2.7 million active patients registered. Recently a validation study was conducted by Lewis *et al* (2007) which concluded that "THIN data that are collected outside of the Clinical Practice Research Datalink (CPRD) appear as valid as the data collected as part of the CPRD".

As the primary aim of the collection of data in the THIN database is patient management, data will reflect only those events that are deemed to be relevant to patient's care. In addition; use of THIN data is not appropriate in studies where individual ethnicity, occupation, employment, and/or socio-economic status are important variables. As for all prescription databases, over-the-counter (OTC) drug use and non-compliance to medication prescriptions might be an issue. As the average follow-up within the THIN database is 5.5 years, the THIN database is not suitable to conduct long-term follow-up studies. Approval needs to be obtained for each study from the THIN governance board.

### 9.4.4. Aarhus Database

The Aarhus University Prescription database comprises clinical and prescription data on the population of former North-Jutland, Aarhus, Rinkjebing and Viborg counties, which since 2007 are called the Central Denmark Region and the North Denmark Region. This population covers a total of 1.8 million inhabitants and is representative of the population of Denmark (Ehrenstein, 2010). Data available on these subjects comprise their eligibility, dispensing data, hospitalizations and procedures and the population can also be linked to other National Danish registries. Dispensing data comprise the filled prescriptions for all ambulatory patients and contains information on name of the drug, ATC code, package identifier (strength and route of administration), and the date of refill. These data can be linked to the national registry of patients that comprises information on admissions to Danish somatic hospitals, emergency rooms and outpatient clinics, diagnosis codes and procedures are registered. These databases have been used in numerous studies and are proven valid for pharmaco-epidemiological research (Ehrenstein, 2010). The study must be announced at the governance committee.

### 9.4.5. SIDIAP Database

GPs play an essential role in the public health care system of Spain, as they are responsible for primary health care, long-term prescriptions and specialist and hospital referrals. The Spanish public health care system covers more than 98% of the population. SIDIAP Database comprises of electronic medical records of a representative sample of patients attended by GPs in Catalonia (North-East Spain), covering a population of more than 5.1 million patients (about 80% of the total of 7.5 million population of Catalonia) from 274 primary care practices with 3,414 participating GPs. The SIDIAP data comprises the clinical and referral events registered by primary care health professionals (GPs and nurses) and administrative staff in electronic medical records, comprehensive demographic information, prescription and corresponding pharmacy invoicing data, specialist referrals, primary care laboratory test results, and hospital admissions and their major outcomes.

Health professionals gather this information using ICD-10 codes, and structured forms designed for the collection of variables relevant for primary care clinical management, such as country of origin, sex, age, height, weight, body mass index, tobacco and alcohol use, blood pressure measurements, blood, and urine test results. Only GPs who meet quality control standards can participate in the SIDIAP database. Encoding personal and clinic identifiers ensures the confidentiality of the information in the SIDIAP Database. Recent reports have shown the SIDIAP data to be useful for epidemiological research ([Garcia-Gil Mdel, 2011](#)). Studies performed using SIDIAP data require previous approval by both the Scientific and the Ethics Committee.

### 9.5. Study size

As this study will be carried out using routinely collected data, all eligible participants will be included. Based on feasibility counts from all data providers, the number of prevalent (already users in 2011) and incident (non-users in 2011) users of strontium ranelate in the proposed sources of data in the year 2012 are provided in Table (9.5) 1. After study start the exact numbers of included and excluded persons will be known over the entire period. We expect to have more than 100,000 prevalent and over 30,000 incident SR users over the study period.

**Table (9.5) 1 - Number of SR users in available data sources in 2012**

Country	Data source	Denominator	Incident users			Prevalent users		
			Total	Men	Women	Total	Men	Women
Italy	HSD	1.5 million	1209	80	1129	10129	613	9616
Spain	SIDIAP	5.1 million	4008	383	3625	14502	917	13585
UK	THIN	3.5 million	514	65	449	2563	255	2308
DK	Aarhus	1.8 million	46	5	41	464	42	412
NL	IPCI	1.2 million	42	1	41	106	14	92
TOTAL		13.1 million	5819	534	5285	27764	1841	26013

### 9.5.1. RMM effectiveness study

[figure not shown]
Based on published studies, the combined prevalence of MI, CVD and PAD before the DHPC published in May 2013 is assumed to be of 19.2% in female and 29.5% in male new users of SR (Abrahamsen, 2014).

A total of **320** male users of SR will suffice to estimate with a 95% confidence and an absolute precision of  $\pm 0.05$ , an unchanged prevalence of MI/CVD/PAD of 29.5%. Similarly, **239** female SR users would suffice to estimate with a 95% confidence and an absolute precision of  $\pm 0.05$ , an unchanged prevalence of MI/CVD/PAD of 19.2%.

Regarding the prevalence of new indication/restrictions of use (severe osteoporosis, and second line therapy), recent data suggest that the prevalence of these would range from 13.0% (Svanstrom, 2014) to 53.1% (Abrahamsen, 2014) for previous fragility fracture (severe osteoporosis), and from 40.4% (Svanstrom, 2014) to 47.9% (Abrahamsen, 2014) for the use of SR as a second line anti-osteoporosis treatment. Given this, 383 users of SR would suffice to estimate (with 95% confidence and 5% precision) an unchanged prevalence of 53.1% (most conservative scenario) for both indications. Lower numbers would be needed if this prevalence either increases or decreases (See Figure (9.5.1) 1).

A number of scenarios with different possible prevalence rates of MI/CVD/PAD, previous osteoporotic fracture, and use as a second line anti-osteoporosis therapy amongst SR users in subsequent years in the period before the publication of the DHPC in May 2013 (*reference*) and after the publication of the second DHPC from April 2014 onwards (*assessment* period) are presented in Figure (9.5.1) 1.

**Figure (9.5.1) 1 - Number of SR users required to estimate the prevalence of contraindications or new indication/restrictions with a 5% absolute precision**

[figure not shown]
For the interrupted time series analyses (see details below), sample size calculations are related to the estimation of the number of observations or time points at which data will be collected. According to the quality criteria of Ramsey et al, at least 10 pre- and 10 post-intervention data points would be needed to reach at least 80% power to detect a change (if the autocorrelation is  $>0.4$ ) (Ramsay, 2003). Our outcomes will be estimated at monthly intervals to ensure that  $>10$  data points are available for both the pre-defined *reference* and *assessment* analysis periods.

### 9.5.2. Safety study

Bearing in mind that the number of incident users identified in 2012 is of 5,819 patients, we expect that at least 30,000 incident SR users will be included for the period 2004-2012, and a lower number of people (500 to 1,000 per annum) will be eligible for the prospective cohort of incident users as identified in 2013-2015 due to the DHPC, making a total of 31,500 to 33,000 SR users. With the combined prevalence of exclusion criteria described above (29.5% for men and 19.2% for women) (Abrahamsen, 2014) and a 90% participants being of female gender (based on feasibility counts for 2012 in Table (9.5) 1), a minimum of 25,128 incident SR users would be included. Considering a prevalence of SR use of 20% in osteoporotic treated population, around 125,640 incident bisphosphonate users are expected, making a total of over 150,000 study participants.

We assume a conservative annual incidence rate of acute myocardial infarction of 0.19/100 person-years in the general population of participants in EU-ADR databases (Coloma, 2013). Based on this and assuming an average follow-up period after cohort entry of 2 years we would expect 570 cases. Accepting an alpha risk of 0.05, with 90% power, and a prevalence of SR use of 20% amongst controls, **415** MI cases and a 1:10 case-control ratio (**4150** controls) would suffice to recognize as statistically significant an odds ratio greater than or equal to 1.5. Different scenarios of SR use ranging from 10% to 40% and the corresponding number of MI cases required for an  $OR \geq 1.5$  (at fixed alpha 0.05, power 90%) are shown in Figure (9.5.2) 1.

[figure not shown]
**Figure (9.5.2) 1 - Number of MI cases required to ensure 90% power to detect as significant an  $OR \geq 1.5$  for the association between SR use and MI.**

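### Section 9.5.2 counts the SR users twice: 125,640 is the whole cohort at a 20% SR share, so about 477 MI cases are expected, not 570, although the 90% power claim still holds

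*Protocol*

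**What the plan says.** Protocol section 9.5.2 builds the size of the comparative safety study in one chain.

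- It projects incident SR users, "making a total of 31,500 to 33,000 SR users".
- It removes ineligible patients: "With the combined prevalence of exclusion criteria described above (29.5% for men and 19.2% for women"), with "a 90% participants being of female gender (based on feasibility counts for 2012 in Table (9.5) 1"). The result is that "a minimum of 25,128 incident SR users would be included".
- It then derives the comparator: "Considering a prevalence of SR use of 20% in osteoporotic treated population, around 125,640 incident bisphosphonate users are expected". To these it adds the SR users, "making a total of over 150,000 study participants".
- For events it writes "We assume a conservative annual incidence rate of acute myocardial infarction of 0.19/100 person-years" and, "assuming an average follow-up period after cohort entry of 2 years we would expect 570 cases".
- It sets 415 MI cases with ten controls each as enough for an odds ratio of 1.5, at alpha 0.05, 90% power and 20% SR use among controls.

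The exclusions for the comparative study are in section 9.2.5.3. They are IHD, PAD, cerebrovascular disease, uncontrolled hypertension and Paget's disease, plus previous VTE for the VTE outcome.

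**The concern.** A share of 20% in the treated population fixes the total once the SR count is known, and the comparator is what remains after SR is taken out. The protocol uses the total as the comparator. Its stated cohort then has an SR share below the 20% that the same section uses to obtain 415 required cases. The 570 expected cases carry the same error.

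The comparison of 570 with 415 is the protocol's only sizing of the comparative safety objective. A reader who relies on it sees more participants and more spare cases than the inputs give.

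**Working it through.** **Inputs, all from section 9.5.2:** 31,500 to 33,000 SR users before exclusions; exclusion prevalence 19.2% in women and 29.5% in men; 90% women; SR share 20%; MI rate 0.0019 per person-year; mean follow-up 2 years; 415 cases required. Alpha is taken as two-sided, which the protocol does not state.

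**Reproducing the protocol's figures**

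- Excluded fraction: 0.9 × 0.192 + 0.1 × 0.295 = 0.2023.
- Eligible SR users: 31,500 × (1 − 0.2023) = 25,128, as stated.
- 25,128 / 0.20 = 125,640, the figure labelled as BP users.
- 25,128 + 125,640 = 150,768, the total of over 150,000.
- 150,000 × 2 × 0.0019 = 570, as stated (150,768 gives 573).
- SR share of that cohort: 25,128 / 150,768 = 16.7%, not 20%.

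**Reading 1: SR is 20% of the treated population, as the sentence says**

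| | Stated | 31,500 SR users | 33,000 SR users |
|---|---|---|---|
| Eligible SR users | 25,128 | 25,128 | 26,324 |
| BP users | 125,640 | 100,512 | 105,296 |
| Participants | over 150,000 | 125,640 | 131,620 |
| Expected MI cases | 570 | 477 | 500 |

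Without rounding the SR count first, the lower-bound BP figure is 100,510. Against the lower-bound column, the protocol overstates BP users by 25% (125,640 / 100,512), participants by 20% (150,768 / 125,640) and cases by about 19% (570 / 477). The surplus over 415 is 477 − 415 = 62 instead of 570 − 415 = 155.

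**Reading 2: 125,640 BP users is kept and the SR share is 16.7%**

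For exposure p0 in controls, the exposure in cases at OR 1.5 is p1 = 1.5·p0 / (1 + 0.5·p0). With k = 10 controls per case and pooled exposure p = (p1 + k·p0)/(k + 1), the number of cases is

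n = [1.96·√((1 + 1/k)·p(1 − p)) + 1.2816·√(p1(1 − p1) + p0(1 − p0)/k)]² / (p1 − p0)².

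- p0 = 0.20, p1 = 0.2727: n = 385.
- p0 = 0.1667, p1 = 0.2308: n = 436.

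The ratio is 436 / 385 = 1.13. The protocol's 415 is not reproduced exactly: this formula gives 385, the continuity correction 400, and the unpooled-variance version 426. The ratio is therefore applied to the stated number: 415 × 1.13 ≈ 470 required. Against 573 expected, the surplus is about 100.

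**Power for OR 1.5 (same approximation, ten controls per case)**

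| Cases | SR use in controls | Power |
|---|---|---|
| 570 (as stated) | 20% | about 97% |
| 477 (reading 1) | 20% | about 95% |
| 573 (reading 2) | 16.7% | about 96% |
| 477 (both unfavourable) | 16.7% | about 92% |

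**The 25,128 as a minimum.** The 19.2% and 29.5% come from the Danish registry study described in sections 7.3 and 9.5.1, and cover cardiac, peripheral arterial and cerebrovascular history only. Uncontrolled hypertension and Paget's disease are also exclusions in section 9.2.5.3 and are not deducted.

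**The case against.** The best defence is that 20% was meant as SR users per BP user. Then 125,640 is the comparator and 150,768 the total. The arithmetic allows this, but the sentence describes a prevalence within the treated population, and the required cases are computed at 20% among controls, not 16.7%. One of the two figures has to change either way.

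Several other points stand and limit the weight of the finding.

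- Section 9.5 includes all eligible patients and says that exact numbers will be known after study start. No recruitment target rests on 150,000 or 570.
- Section 9.5.2 says that its figure gives required cases for SR use from 10% to 40%, a range that covers 16.7%.
- The 477 uses the lower bound of the SR projection. The protocol also calls its MI rate conservative. That rate is for the general population of the databases, whereas the cohort is aged 50 or older (section 9.2.4).
- Starting from 31,500 explains the word *minimum* in part.

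A reader might infer that the study is underpowered. The documents do not support that: expected cases exceed required cases on both readings, and 477 also exceeds the 426 of the most demanding formula tried at 20%.

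A reader might also infer that the undeducted exclusions would use up the surplus. The protocol gives no prevalence for uncontrolled hypertension under its three-part definition or for Paget's disease, and no overlap with the vascular conditions already removed. The size of that deduction cannot be derived.

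**Conclusion.** The error is real and confined to stated figures: the total cohort is labelled as the comparator and the SR users are counted a second time. With SR at 20% of treated patients, the surplus of expected over required MI cases falls by 60% (93 of 155); on the ratio reading it falls by about a third. The 90% power statement survives on both.

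This rests on the protocol's own SR projection, MI rate and follow-up, on 415 as the requirement, on a two-sided alpha, and on an unmatched normal approximation for power. It concerns the overall MI analysis only and says nothing about power within each period.

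The wording of 25,128 as a minimum is a secondary point of unknown size. Overall this is a minor to moderate text correction.

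**What to change.** Choose one reading in section 9.5.2 and make the paragraph consistent.

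1. If SR is 20% of the treated population, state about 100,510 BP users, about 125,640 participants and about 477 expected MI cases, with about 131,600 participants and 500 cases at the upper SR count. Keep 415 at 20%.
2. If 125,640 BP users is an independent count, or 20% is an SR:BP ratio, say so and give the source. Recompute the required cases at 16.7% SR use (about 470) and set them against about 573 expected.

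In either case, describe 25,128 as *about*, or deduct uncontrolled hypertension and Paget's disease once database counts are available.

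The cost is a text edit and a less generous stated surplus. Data extraction, eligibility and analysis are unaffected.

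### At 20% strontium ranelate use, 125,640 is the whole safety cohort, not the bisphosphonate users, so the expected MI cases are about 477 rather than 570

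*Protocol*

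**What the plan says.** The calculation is one chain in Protocol Section 9.5.2.

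- Incident SR users over the study: "making a total of 31,500 to 33,000 SR users".
- Contraindicated patients are removed at 29.5% of men and 19.2% of women, with "a 90% participants being of female gender". The result is that "a minimum of 25,128 incident SR users would be included".
- Comparator: "Considering a prevalence of SR use of 20% in osteoporotic treated population, around 125,640 incident bisphosphonate users are expected". The SR users are then added, which puts the cohort above 150,000.
- Events: a "conservative annual incidence rate of acute myocardial infarction of 0.19/100 person-years" is applied, and then "Based on this and assuming an average follow-up period after cohort entry of 2 years we would expect 570 cases".
- Requirement: with alpha 0.05, 90% power, 20% SR use among controls and ten controls per case, 415 MI cases are said to be enough to detect an odds ratio of 1.5.

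Section 9.1 restricts the safety cohort to new users of SR or of oral bisphosphonates. SR and BP users together therefore make up the whole cohort.

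**The concern.** If SR users are 20% of the treated population, there are four BP users for each SR user. The protocol has five, because it treats the SR count divided by 0.20 as the BP group when it is the total. The SR users are then counted twice.

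The expected case count is built on that inflated total. Comparing 570 expected with 415 required cases is the only quantitative support in the protocol for the 90% power statement. The two sides of the comparison also rest on different SR shares: the cohort behind the 570 implies 16.7%, while the 415 assumes 20%. Both cannot be true of one cohort from which the controls are drawn.

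**Working it through.** **Inputs, all from Section 9.5.2:** 31,500 SR users (lower bound); exclusions 29.5% (men) and 19.2% (women); 90% women; SR share 20%; MI rate 0.19 per 100 person-years; 2 years' mean follow-up; 415 cases required at odds ratio 1.5, 20% exposure and 1:10 matching.

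**1. Reproducing the stated figures**

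- Eligible SR users: 31,500 × (0.9 × 0.808 + 0.1 × 0.705) = 31,500 × 0.7977 = 25,127.6, stated as 25,128.
- Stated BP users: 25,128 / 0.20 = 125,640 exactly.
- Stated total: 25,128 + 125,640 = 150,768, the figure behind the stated total of over 150,000.
- Stated cases: 150,000 × 2 × 0.0019 = 570 exactly.

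**2. Keeping the 20% share**

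| Quantity | Stated | At a 20% SR share | Overstatement |
|---|---|---|---|
| BP users | 125,640 | 125,640 − 25,128 = 100,512 | 25% |
| Participants | 150,768 | 25,128 / 0.20 = 125,640 | 20.0% |
| Expected MI cases | 570 | 125,640 × 2 × 0.0019 = 477.4 | 19.4% |

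The margin over 415 falls from 570 − 415 = 155 cases (37%) to 477 − 415 = 62 (15%). Expected cases would drop below 415 at a rate of 415 / (125,640 × 2) = 0.165 per 100 person-years, against 0.138 with 150,000 participants. The corresponding mean follow-up is 415 / (125,640 × 0.0019) = 1.74 years, against 1.46.

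**3. Keeping 125,640 BP users instead**

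- SR share: 25,128 / 150,768 = 16.7%.
- Expected cases: 150,768 × 2 × 0.0019 = 573.
- The requirement must then be recomputed at 16.7% exposure. With p0 the exposure in controls, p1 = 1.5·p0 / (1 − p0 + 1.5·p0), k = 10 and p̄ = (p1 + k·p0)/(k + 1), the usual two-proportion formula is

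  n = [1.960·√((1 + 1/k)·p̄(1 − p̄)) + 1.282·√(p1(1 − p1) + p0(1 − p0)/k)]² / (p1 − p0)².

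- At p0 = 0.20, p1 = 0.2727 and n = 385. At p0 = 0.1667, p1 = 0.2308 and n = 436. The ratio is 1.13, which scales the protocol's 415 to about 470.

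The 415 is not reproduced exactly. At 20% exposure this formula gives 385, its continuity-corrected form 400, and the unpooled-variance form 426. At 16.7% the same three give 436, 453 and 489.

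**4. Power for odds ratio 1.5** (same formula, two-sided 0.05, no continuity correction)

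| Cases | SR share among controls | Power |
|---|---|---|
| 570 | 20% | 0.975 |
| 477 | 20% | 0.949 |
| 573 | 16.7% | 0.958 |

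The protocol does not say whether alpha is one- or two-sided; two-sided is assumed here.

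**The case against.** The strongest reply is that nothing turns on the slip. All eligible patients are included from routine data (Section 9.5), so no recruitment target depends on 125,640 or 570. The requirement of 415 is met under every reading. The inputs are also cautious: 25,128 is given as a minimum, and the upper bound of 33,000 SR users gives 26,324 eligible, about 131,600 in total and about 500 cases. With 125,640 participants, a mean follow-up of 2.4 years would bring the count back to 570. This part stands. The effect is on the stated justification, not on the feasibility of the undivided MI analysis.

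A second reply is that 20% may have been meant loosely as one SR user per five BP users, which would rescue 125,640, 150,000 and 570. The text does not support that. It describes a share of the treated population, and the same paragraph applies 20% to controls, who come from that cohort (Section 9.3.1). Under the one-to-five reading the 20% would have to change instead. The protocol says its figure on required cases spans SR use of 10% to 40%, so the alternative requirement may already be plotted; that figure could not be seen.

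Third, the 15% margin depends on the protocol's 415. Against 385 the margin at 477 would be 92 cases (24%). That is fair, but 415 is the requirement the protocol states, so it is the right yardstick for the protocol's own claim.

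**Conclusion.** The error is real. Section 9.5.2 states a cohort size and an SR share that cannot both hold. Under the share as worded, participants are overstated by 20% and expected MI cases by 19.4% (570 against 477), and the margin over the stated requirement shrinks from 155 cases to about 62.

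The 90% power claim for MI at odds ratio 1.5, with all cases analysed together, is not lost: it is about 95% at a 20% share and about 96% at 16.7%. These results take the protocol's incidence rate, follow-up and lower-bound SR count as given, and use the SR share of the cohort as the exposure prevalence among controls, as the protocol does. The smaller margin still deserves correct reporting, because Section 9.7.3.3 stratifies all relative-risk analyses by period and the calculation covers only the undivided analysis.

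**What to change.** Restate Section 9.5.2 under one SR share:

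- **Keep 20%:** 25,128 SR users plus about 100,500 BP users, about 125,600 participants in total, and about 477 expected MI cases against 415 required; or
- **Keep 125,640 BP users:** give the SR share as 16.7%, the expected cases as about 573, and the requirement recomputed at 16.7% exposure (about 470 if the 415 is scaled; 436 to 489 by formula).

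The first option fits the existing wording and leaves the 415 untouched. The affected figures appear only in Section 9.5.2; the abstract gives no BP count or case count. The cost is two sentences and, under the first option, a less favourable expected case count. Design, data extraction and analysis do not change.
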